# LIST OF ABBREVIATIONS AND ACRONYMS

AE	Adverse Event
ATPmax	Muscle mitochondrial phosphorylation capacity by  P Magnetic
	Resonance Spectroscopy (MRS)
CKD	Chronic kidney disease
EAE	Expedited Adverse Event
ETC	Electronic Transport Chain
EC	ethics committee
eGFR	Estimated Glomerular Filtration Rate
FDA	(United States) Food and Drug Administration
GCP	Good Clinical Practices
IDS	UW Investigational Drug Services
IRB	Institutional Review Board
KRI	Kidney Research Institute
LDMS	Laboratory Data Management System
LL	Local Laboratory
MRS	 P Magnetic resonance spectroscopy
NAD+	
NIDDK	United States) National Institute of Diabetes and Digestive and Kidney
NIH	(United States) National Institutes of Health
NR	Nicotinamide Riboside
ROC	Regulatory Operations Center
SAE	Serious Adverse Event
SUSAR	Suspected Unexpected Serious Adverse Reaction
SOP	Standard Operating Procedures
SSP	Study Specific Procedures
TA	Tibialis anterior leg muscle
TCA	Tricarboxylic acid (Krebs) cycle

#### **SCHEMA**

Purpose:	Study the impact of oral nicotinamide riboside vs CoQ10 on aerobic capacity, muscle performance and mitochondrial metabolism among persons with moderate-severe CKD.
Design:	Randomized, placebo controlled cross-over trial
Study Population:	Adults age 30-79 with moderate-severe CKD eGFR by CKD (EPI equation) $< 50 ml/min/1.73 m^2$
Study Size:	30 (10 in each of 3 arms).
Treatment Regimen:	
 
Nicotinamide riboside 1000mg daily (250mg - 2 tablets twice daily)
 
Coenzyme Q10 1200mg daily (600mg - 1 tablets twice daily)
 
Placebo (sugar pill)
 

Study Duration:	1.5-2 year

#### Primary Objectives:

- To test if NR or CoQ10 supplementation improves aerobic capacity by cycle ergometry testing compared with placebo.
- To test if NR or CoQ10 improves muscle work efficiency by bicycle ergometry.

#### **Secondary Objectives:**

[figure not shown]
- To test if NR or CoQ10 improves peripheral blood monocyte bioenergetics health.
- To test the effects of oral NR or CoQ10 supplementation on metabolic response profile.
- To test if NR or CoQ10 supplementation reduces inflammatory and oxidative stress biomarkers.
- To test if NR or CoQ10 improves subjective fatigue, self-reported physical function, and heart failure symptoms.

#### **Exploratory objective:**

• In-vivo mitochondrial energetics by Phosphorus Magnetic Resonance Spectroscopy (MRS) investigating phosphorylation capacity (ATPmax)

# SCHEMA

# **1.0 INTRODUCTION**

# 1.1 Background and Prior Research

**Sarcopenia is a common complication of chronic kidney disease.** Sarcopenia is defined by decreased muscle mass or function and is central to the frailty phenotype that is associated with disability, hospitalization, and death. Studies have shown that altered metabolism in CKD leads to well-described catabolic and pro-inflammatory processes with adverse consequences for lipid, amino acid, and protein metabolism that are linked to overall energy metabolism^5. These events consequently lead to an impaired insulin response, contributing to significant comorbidity among patients living with CKD.

**Sarcopenia alters glucose metabolism**. Insulin resistance in CKD can contribute to catapleurosis, which in turn increases reliance on the muscle amino acid pool for mitochondrial tricarboxylic acid-cycle respiratory fuel. These events culminate, ultimately, in muscle breakdown, sarcopenia, weakness and fatigue, increasing risk of mobility, disability and frailty.

**CKD and sarcopenia alter metabolic pathways.** Metabolomic profiling of CKD compared to controls under conditions of fasting and insulin clamp testing reveal marked aberrancy in CoQ10 biosynthesis pathways and niacinamide metabolism respectively. This suggests impaired mitochondrial metabolism as a major contributor in insulin resistance (figure 1). We have observed fasting-state pathway differences in ubiquinone (Coenzyme Q) biosynthesis among patients with CKD compared to controls, suggesting alteration in the integrity or efficiency of the electron transport chain (ETC) of the mitochondria, in turn predisposing to mitochondrial oxidant production resulting in insulin resistance.

**Deficiency in CoQ10 levels has been associated with oxidative stress and impaired oral glucose tolerance in pre-clinical models**. This may explain the observed uncoupling of muscle mitochondrial oxidative phosphorylation and oxidative stress in CKD. CoQ10 administration in advanced kidney disease patients improved oxidative stress with reduction in isofuran levels (products of lipid peroxidation). However, little is known about its effects on oxidative stress and mitochondrial function via assessment of mitochondrial bioenergetics using high throughput respirometry assessments in moderate-sever CKD not requiring dialysis.

**Nicotinamide Riboside (NR) is implicated in mitochondrial dynamics in those with CKD.** NAD+ is important in mitochondrial biogenesis, bioenergetics and redox homeostasis through NADP+. Indeed, administration of nicotinamide riboside (NR), a natural NAD precursor, has been shown to improve insulin sensitivity in obese mice, as well as increase NAD levels, leading to augmented mitochondrial sirtuin (SIRT3) activity and improve muscle endurance along with muscle mitochondrial content. Among patients with CKD not treated with dialysis, insulin clamp testing revealed marked plasma abnormalities in pathways important for mitochondrial TCA cycle function and antioxidant capacity compared with controls. Disruption in insulin response was most notable for nicotinamide metabolism among participants with CKD compare to controls, with a markedly blunted decrease in nicotinamide after insulin challenge. These findings implicate disruption in niacinamide metabolism as a potential mechanism underlying impaired insulin resistance and mitochondrial metabolism in CKD. Here we propose a phase 2 placebo controlled randomized cross-over trial of nicotinamide riboside and Coenzyme Q10 in CKD investigating the impact on both metabolic and functional consequences using targeted metabolomics, assessment of mitochondrial bioenergetics and bicycle ergometry.

[figure not shown]

Figure 1. Left panel: Fasting-state metabolic pathway analysis comparing CKD to controls. Right panel: Metabolic pathway differences with insulin challenge comparing CKD to control.

### 1.2 Rationale

Sarcopenia is common in CKD patients and is associated with adverse metabolic and clinical outcomes. Existing evidence and our preliminary data suggest that mitochondrial dysfunction is a key mechanism underlying sarcopenia in CKD. However, major gaps exist in our understanding of these processes and their physical and social impacts. Altered CoQ10 and NR have both been implicated in mitochondrial dysfunction. Preliminary evidence suggests supplementation may ameliorate these altered metabolic processes. Addressing these knowledge gaps is necessary to shed new light on the pathophysiology of sarcopenia in CKD and suggest future interventions that reduce morbidity and mortality.

### 1.3 Abstract

Skeletal muscle dysfunction (sarcopenia) is an under-recognized target organ complication of CKD with substantial adverse clinical consequences of disability, hospitalization, and death. Sarcopenia in this proposal is defined by impaired metabolism and physical function associated with decreased skeletal muscle mass or function. Skeletal muscle tissue relies on mitochondria to efficiently utilize oxygen to generate ATP. Impaired mitochondrial energetics is a central mechanism of sarcopenia in CKD. Coenzyme Q10 and Nicotinamide Riboside deficiencies have been implicated in altered mitochondria function, but greater knowledge is needed. We hypothesize that supplementation with oral CoQ10 and

NR will enhance mitochondrial function measured through aerobic capacity, muscle work efficiency, and metabolic profile using cycler ergometry and targeted metabolomics. Secondarily, we seek to describe the impact of these interventions on ex-vivo measures of mitochondrial metabolism, biomarkers of oxidative stress, inflammation and functional outcomes of muscle efficiency by cycle ergometry as well as patient reported fatigue among persons with chronic kidney disease. Lastly, in-vivo muscle mitochondrial phosphorylation capacity by P Magnetic resonance spectroscopy (MRS) will test exploratory aspects and descriptive measures of mitochondrial function.

# 2.0 STUDY OBJECTIVES AND DESIGN

# 2.1 Primary Objectives

The primary objectives of this study are to:.

- To test if NR or CoQ10 supplementation improves aerobic capacity by cycle ergometry testing compared with placebo.
- To test if NR or CoQ10 improves muscle work efficiency by bicycle ergometry

# 2.2 Secondary Objectives

The secondary objectives of this study are to:

- To test if NR or CoQ10 improves peripheral blood monocyte bioenergetics health.
- To test the effects of oral NR or CoQ10 supplementation on metabolic response profile.
- To test if NR or CoQ10 supplementation reduces inflammatory and oxidative stress biomarkers.
- To test if NR or CoQ10 improves subjective fatigue, self-reported physical function, and chart failure symptoms.

# 2.3 Study Design

**Overview of study design:** This is a placebo-controlled, double-blind crossover trial with 3 arms: placebo, NR, and CoQ10. There are 2 phases 56 days each separated by a 1-week washout period.

A brief screening visit will assess eligibility criteria, and will include informed consent. Qualified participants will be randomly assigned (1:1) to 56 days of placebo followed by 7 days NR or CoQ10, followed another 7 day washout followed by 56 days of either NR or CoQ10. Qualified participants will participate in at least 4 study visits, plus a screening visit. An optional P MRS study visit to assess in vivo muscle mitochondrial phosphorylation capacity will be offered to those who qualify. Including the separate MRS visit will increase the total visits to 8. Study outcomes will be assessed at each of these 4 major visits.

Subjects will receive 1000mg of Nicotinamide riboside (Tru Niagen) or coenzyme Q10 (1200mg/day) for 8 weeks. This dose was chosen based on a review of studies in the literature evaluating biological activity. Placebo will consist of identical appearing tablet.

Objectives	Population	Exposure	Design	Outcome
Primary- To test if NR or CoQ10 supplementation improves aerobic capacity and muscle performance	Mod-severe CKD with eGFR < 50 mL/dL (N=30)	Randomized order CoQ10 or NR or Placebo	Placebo-controlled double-blind control crossover	VO2max and Work efficiency
Secondary- To test NR or CoQ10 on descriptive measures of mitochondrial and metabolic functioning	Mod-severe CKD with eGFR < 50 mL/dL (N=30)	Randomized order CoQ10 or NR or Placebo	Placebo-controlled double-blind control crossover	
 
-monocyte bioenergetics (Reserve capacity)
 
-ATPmax (MRS Imaging)
 
-Blood metabolomics & biomarkers
 
-Fatigue & Heart questionnaires
 

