# 3.0 STUDY POPULATION

Study participants will be selected from patients with moderate-severe CKD not treated with dialysis from the Muscle Mitochondrial Energetics and Dysfunction (MEND) study, a cross-sectional clinic-based study of CKD. Additional patients may be recruited from nephrology clinics in the University of Washington System including Harborview Medical center, and University of Washington Medical Center.

Participants will be selected for this study from the indicated populations according to the criteria in Section 3.1 and 3.2. They will be recruited, screened, and enrolled as described in Section 3.3 [and assigned to a study treatment/intervention group as described in Section 7.4]. Issues related to participant retention and withdrawal from the study are described in Sections 3.5 and 3.6, respectively.

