# 4.0 STUDY TREATMENT/PRODUCT/INTERVENTION

### 4.1 Treatment/Product/Intervention Regimen(s):

Participants will be randomized to in treatment order to receive the following medications for 6 weeks plus an additional 1 week in case of logistical difficulties with scheduling study visits.

- Nicotinamide Riboside (Tru Niagen by Chromodex) at 1000mg/day in the form of two 250mg tablets twice daily.
- Coenzyme Q10 will be administered at 600mg twice daily.
- **Placebo** will consist of identical appearing pill. This will be a double dummy with 4 tablets appearing identical to NR and 2 tablets appearing identical to CoQ10.

Randomized Tx Order 1 st , 2 nd , 3 rd	Total Dosage QD	Regimen	Duration
Nicotinamide Riboside	1000 mg	250 mg tabs x2 BID	6 weeks (+/- 7 days)
Coenzyme Q10	1200 mg	600 mg tabs BID	6 weeks (+/- 7 days)
Placebo	N/A	BID	6 weeks (+/- 7 days)

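### Section 2.3 puts placebo first in a two-phase design, against the three randomised periods elsewhere; if followed, neither drug–placebo contrast could be estimated with the planned period effect

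*Combined protocol and SAP*

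**What the plan says.** Section 2.3 opens by describing a "crossover trial with 3 arms: placebo, NR, and CoQ10". It then states: "There are 2 phases 56 days each separated by a 1-week washout period". Its allocation sentence has participants "randomly assigned (1:1) to 56 days of placebo followed by 7 days NR or CoQ10", then a further washout, then 56 days of one of the two drugs. The table that closes the same section gives the exposure as "Randomized order CoQ10 or NR or Placebo".

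These passages support three periods in randomised order:

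- Section 4.1: "Participants will be randomized to in treatment order to receive the following medications for 6 weeks". Its regimen table ranks the three treatments first, second and third.
- Section 5.0 and Table 1: three treatment columns, end-of-period visits at weeks 6, 13 and 20, and washouts at weeks 7 and 14.
- Table 2 in section 7.3: six named sequences of five participants each. This is the only place where the sequences are listed.
- Section 7.6.1: a 3 × 3 crossover, which implies three periods but not six sequences.

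These passages carry two-group or two-period wording:

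- Section 7.3 has one sentence calling the study a crossover of two treatments, directly after a sentence giving three.
- Section 7.4 has participants randomised into two groups, and gives no sequences, ratio or blocking. Section 3.0 relies on it: participants are "assigned to a study treatment/intervention group as described in Section 7.4".
- Section 7.1 (washout between treatment and placebo) and section 7.6.1 (carryover from the first period to the second) are less clear-cut.

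**The concern.** The primary objective in section 2.1 is "To test if NR or CoQ10 supplementation improves aerobic capacity by cycle ergometry testing compared with placebo", and section 7.6.1 plans an ANOVA with sequence, treatment and period effects. If everyone takes placebo first, placebo and period 1 are the same thing. A model with a period effect then cannot separate drug from time.

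Dropping the period effect would make the contrasts computable, but any training or time effect between the tests compared would be credited to the drug. The protocol treats training effects as a real concern, because section 5.0 adds a practice ride to reduce them, but it gives no size for them.

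The pharmacy runs the randomisation (sections 4.2 and 7.4). A reader who goes to the design section or the assignment section for instructions would not find the six sequences in either.

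**Working it through.** **Inputs.** N = 30, two-sided 0.05, 80% power and an SD of the within-participant difference of 2.1 ml/kg/min (section 7.3). Six sequences of 5 (Table 2). Sequence, treatment and period effects (section 7.6.1). Up to 36 recruits (section 4.3).

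**The plan's own figures.** A paired noncentral t calculation (n − 1 df) reproduces all six entries of Table 3: 34, 16 and 10 at 80% power; 44, 21 and 13 at 90%. The sample size therefore treats the comparison as a clean within-participant difference, with nothing lost to period.

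**Estimability under the 2.3 text.** Let π be the period effects and τ the treatment effects. With two phases, the within-participant differences (phase 2 minus phase 1) have these expectations:

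- NR group: (π₂ − π₁) + (τ_NR − τ_P)
- CoQ10 group: (π₂ − π₁) + (τ_CoQ10 − τ_P)

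There are two equations and three unknowns. Only τ_NR − τ_CoQ10 can be recovered.

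The same argument covers three periods with placebo first. Add any constant k to both drug effects and subtract k from the effects of every period after the first. Every expected value is unchanged, because drugs occur only in those later periods and placebo never does. The data cannot determine k, so neither drug–placebo contrast is estimable. Adding the baseline test does not help, because it too lies outside the drug periods.

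A rank test of the design matrices, with categorical period effects, agrees:

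| Design | NR − placebo | CoQ10 − placebo | NR − CoQ10 |
|---|---|---|---|
| Two phases, placebo first | no | no | yes |
| Three periods, placebo first | no | no | yes |
| Either of these plus baseline | no | no | yes |
| Table 2, six sequences | yes | yes | yes |

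**Precision under Table 2.** The within-participant variance is σ² = 2.1²/2 = 2.205. Each treatment occurs 10 times in each period, so adjusting for period costs no variance. SE = √(2 × 2.205/30) = 2.1/√30 = 0.383. With 90 − 30 − 2 − 2 = 56 df, the difference detectable at 80% power is 1.09 ml/kg/min (1.11 as a paired t with 29 df).

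**Precision under the two-phase text.** The only estimable contrast, NR versus CoQ10, becomes a comparison between participants. SE = 2.1 × √(1/15 + 1/15) = 0.767. With 28 df the detectable difference is 2.23 ml/kg/min.

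**Allocation list (for the fix).** Simple equal-probability allocation of 30 gives exactly 5 per sequence with probability 30!/(5!⁶ × 6³⁰) = 0.0004. A blocked list of 36 gives 6 per sequence. If 6 are then lost at random, the chance of exactly 5 each is 6⁶/C(36,6) = 0.024, but the variance of a placebo contrast rises by at most about 4% over a balanced 30.

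**Table 2 letters.** Rows 1–2 imply B = CoQ10 and C = NR; rows 3–6 imply the reverse. No single key fits all six rows.

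**The case against.** The strongest reply is that this is a drafting conflict and not a flawed design. The 2.3 sentence cannot be run as written: it refers to another washout when none has been stated before it. The operational passages agree on three periods. This stands, and it is why the harm is conditional.

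A second reply is that a garbled sentence may have lost words such as a reversal of order. Two phases with the drug–placebo order randomised would make the drug–placebo contrasts estimable, with a variance of about 0.134σ² against 0.067σ² under Table 2. The text does not say this. Likewise, a linear time trend in place of categorical periods would rescue the three-period placebo-first reading, at 0.217σ² (about 3.25 times the Table 2 variance), but the plan does not state one and it would not rescue the two-phase reading.

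Third, some of the listed conflicts are weak, and this is fair. Ten per arm in the schema and section 4.3 can be read as ten per first treatment, which fits Table 2's N column. The 7.1 and 7.6.1 wording can be read generically. The letter mismatch leaves the same six sequences of five under either key. The solid conflicts are the 2.3 text, the two-treatment sentence in 7.3 and the two groups in 7.4.

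Finally, no passage plans simple randomisation, so the 0.0004 figure supports a blocked list but shows no error in the plan.

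**Conclusion.** The concern holds, and the text should be fixed. The contradiction is certain from the text, and no governing passage resolves it, because the section named for assignment does not give the sequences.

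If 2.3 were implemented, 0 of 2 drug–placebo contrasts would be estimable, against 2 of 2 under Table 2. That result rests on placebo coming first and on period being categorical, which is the natural reading of the planned ANOVA. The standard errors also assume a participant term (7.6.1 does not name one), 30 completers, and one SD of 2.1 for every pairwise difference; Table 3 takes that SD from a 12-month exercise programme.

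If period were dropped, the bias would equal the drift between the tests compared. The documents give no drift, so no error rate is claimed. Nothing here shows that the trial was run placebo-first.

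**What to change.** - **2.3:** replace the two-phase, placebo-first text with three treatment periods and randomisation in equal ratio to the six sequences of Table 2.
- **7.4:** refer to six treatment sequences in place of two groups. Preferably specify a blocked list with block sizes in multiples of 6, covering the 36 recruits allowed in 4.3 (6 per sequence). Five completers per sequence is a target only; unequal counts do not affect estimability.
- **7.3:** delete the two-treatment sentence. In Table 2, print one letter key, correct the rows that disagree with it, and check the pharmacy list against the drug names.
- **7.1 and 7.6.1:** refer to washout and carryover between successive treatment periods.
- **Schema and 4.3:** state ten per arm as ten per first-treatment group (two sequences of five).

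The treatment-duration passages also disagree: 56 days or 8 weeks in 2.3 and 2 months in 7.6.1, against 6 weeks in 4.1, 5.0 and Table 1. They must be reconciled separately; no view is taken here on which is right.

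The cost is wording in seven places, one allocation list and one check of the pharmacy list. No participants, visits or procedures are added.

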# 3.0 STUDY POPULATION

Study participants will be selected from patients with moderate-severe CKD not treated with dialysis from the Muscle Mitochondrial Energetics and Dysfunction (MEND) study, a cross-sectional clinic-based study of CKD. Additional patients may be recruited from nephrology clinics in the University of Washington System including Harborview Medical center, and University of Washington Medical Center.

Participants will be selected for this study from the indicated populations according to the criteria in Section 3.1 and 3.2. They will be recruited, screened, and enrolled as described in Section 3.3 [and assigned to a study treatment/intervention group as described in Section 7.4]. Issues related to participant retention and withdrawal from the study are described in Sections 3.5 and 3.6, respectively.

# 3.1 Inclusion Criteria

- Adults between 30 and 79 years of age
- Diagnosis of moderate-severe CKD, defined in this study as an estimated glomerular filtration rate (eGFR) of <50ml/min/1.73m^2 using the Chronic Kidney Disease Epidemiology Collaboration equation
- 6 minute walking distance<500 meters

# 3.2 Exclusion Criteria

- Pregnant
- On chronic dialysis
- Expectation to start dialysis within 6 months
- Insulin dependent diabetes
- Severe anemia: hemoglobin <8gm/dL
- Hyperkalemia: K>5.7
- Kidney transplantation
- Weight >300 lbs
- HIV
- End stage liver disease with cirrhosis
- Oxygen-dependent COPD
- Unable to walk unassisted from room to room in own house
- Institutionalization, or inability to consent
- Use of immunosuppressive medications (i.e. steroids, calcineurin inhibitors)
- Malignancy requiring active treatment or currently under surveillance at the discretion of the investigator
- Pacemaker
- Current participation in another interventional trial
- Non-English speaking
- Hospitalization for heart attack, stroke, or unstable cardiac chest pain in last 3 months (e.g. myocardial infarction, unstable angina, cerebrovascular accident)
- Any severe medical condition that the investigator feels would disqualify a patient from aggressive exercise.
- Baseline systolic blood pressure >170 or diastolic blood pressure >100
- Persistent or permanent uncontrolled arrhythmia at the discretion of the investigator.

